### 3. STUDY ENDPOINTS

As applicable, the 2 (CRC phase) or 3 (Outpatient phase) treatment groups will be compared based on the following primary, secondary and exploratory endpoints.

#### Primary Endpoint:

The primary endpoint is the incidence of hypoglycemia (i.e, blood glucose  $\leq 70 \text{ mg/dL}$ ;  $3.89 \text{ mmol/L}$ ) associated with an exercise session across 12 weeks of outpatient treatment as measured by blood glucose meter (BGM).

For primary endpoint analysis the exercise session must meet the criteria defined in Section 2.4 as being a 'qualified exercise session' by requiring (1) a confirmed blood glucose value of 100-180 mg/dL (5.56 – 10 mmol/L) prior to starting exercise, (2) self-administered the study drug no more than 10 minutes prior to exercise (five minutes is the target), (3) conducted a protocol allowed exercise for moderate to high intensity for at least 30 minutes and no longer than 75 minutes, and (4) achieved a target heart rate of 80% of maximum calculated heart rate at least once during the session.

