10.4. Visit 5 Through 10 – Outpatient Stage

10.4.1. Visits 5 Through 10 – Treatment Day 4-113

During the outpatient stage, subjects will return for clinic visits every two weeks. Activities to be performed at these visits are outlined in the Schedule of Activities ([Table 1](#)[bookmark7](#)).

In the outpatient setting, subjects will perform moderate to high intensity aerobic exercise with a target of at least 2-3 qualifying sessions per week. To be eligible for study drug dosing, the planned aerobic exercise will be 30-75 minutes in duration. Additionally, the subject's BGM must range between 100-180 mg/dL (5.56 – 10 mmol/L) before the exercise session. Subjects must record their carbohydrate intake (eg, both dextrose tabs and carbohydrates from food) 15 minutes before exercise, during the exercise session, and up to 5 hours post-exercise session.

During the exercise session, the subject is to only drink carbohydrate free liquids (e.g., Powerade Zero or comparable product) and will be provided with glucose tabs to use as needed. The subject will take 5 BGM measurements with exercise: at -15 minutes and just before exercise to establish baseline value, at 30 minutes into the exercise session, at the end of the exercise session, and at 30 minutes after the exercise session. There is a ± 2 minute window on all of these time points.

Per ADA guidelines, if a subject's glucose falls to ≤ 70 mg/dL (3.89 mmol/L) during any exercise session, then the exercise session should be stopped, and no more exercise should be completed that same day; the subject should rest, and glucose tabs should be taken every 15 minutes until the hypoglycemia is corrected and euglycemia (confirmed by BGM) is maintained. Subjects will be provided with a supply of glucose tabs and instructed to use these rather than other sources of carbohydrate to treat hypoglycemia.

During the outpatient phase the subject will be provided with the following items for recording study data and will be provided with instructions for use and uploading data to the cloud if applicable.

1. Blood Glucose Meter: Bayer[®] Contour Next One
 - a. Used to collect blood glucose values during exercise sessions and to confirm blood glucose if a value ≤ 70 mg/dL (3.89 mmol/L) is indicated by CGM.
2. Dexcom[®] G5 Continuous Glucose Meter
 - a. Used to collect interstitial glucose measurements on a continuous basis.
3. Fitbit[®] Ionic

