12.4.10. Missing Data

Every effort will be made to limit the number of missing data elements for the study. All study endpoints for the primary and secondary analyses will be reviewed for missing data and appropriate methodology applied if applicable, as described in the SAP. Sensitivity analyses may be performed.

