## **2.2 Handling of Missing Data:**

Imputation of missing data will not be performed.

To handle missing or partial AE and concomitant medication dates, the following rules will be applied.

For partial start dates:

1. If the year is unknown, then do not impute the date but assign a missing value.
2. If the month is unknown, then assign “January.”
3. If the day is unknown, then assign “01.”

For partial end dates:

4. If the year is unknown, then do not impute the date but assign a missing value.
5. If the month is unknown, then assign “December.”
6. If the day is unknown, then assign the last day of the month.

After implementing the rules above, to determine whether AEs (or medications) with missing start or stop dates are pretreatment or on/after treatment, the following strategy will be used:

1. If the start date and stop date are both missing, then the most conservative approach is taken and the AE (or medication) is considered to be treatment emergent (or concomitant medication).

2. If the start date is missing but the stop date is not missing and is on or after the day of study dose administration, then the most conservative approach is taken and the AE (or medication) is considered to be treatment emergent (or concomitant medication).
3. If the start date is missing but the stop date is not missing and is before the day of study dose and after the date of signed informed consent, then the AE (or medication) is considered to be before treatment (or prior medication).
4. If the start date is not missing but the stop date is missing, then the most conservative approach is taken, and medication is considered to be concomitant while the AE is defined by start date.

If the Adverse Event Relationship flag is missing, the relationship for adverse event will be defined as related. If the Adverse Event Severity flag is missing, the severity for adverse event will be defined as severe.

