### **Baseline for Outpatient Phase:**

The Baseline for Outpatient Phase is defined as the latest assessment prior to the first administration of the study drug in the Outpatient Phase for the analysis pertaining to Outpatient Phase, unless otherwise stated.

If the assessment occurs on the same day as the first study drug administration for either of the phases, then the time of assessment should be compared to the time of first dose administration for both CRC and Outpatient Phase.

Baseline will be calculated as the average of the blood glucose measurements (BGMT) at: -15 minutes and just before the exercise session (Time 0).

**Change from Baseline:** The change from baseline values will be calculated as post baseline value minus the baseline value.

If BGM readings are missing from the CRC phase, the YSI readings can be used.

**Shift from Baseline:** The shift from baseline is defined as a change in categorical variable from baseline to subsequent visits for each subject.

**Percentage Change from Baseline:** The percentage change from baseline is defined as the ratio of change (Analysis value – Baseline value) and baseline value expressed in terms of percentage.  
% Change from Baseline =  $((\text{value} - \text{baseline}) / \text{baseline}) * 100$ ;

**Treatment Emergent Adverse Event (TEAE):** TEAE is any AE does not present prior to the initiation of IMP (Investigation Medicinal Product) administration at CRC phase or any event already present that worsens in either intensity or frequency following exposure to the IMP at CRC phase.

An SAE is any AE that results in death, is life-threatening (this refers to an event in which the subject was at risk of death at the time of the event; it does not refer to an event that hypothetically might have caused death had it been more severe), requires inpatient hospitalization or prolongation of existing hospitalization, results in persistent or significant

disability/incapacity, is a congenital anomaly/birth defect, is medically important (this refers to an event that may not be immediately life-threatening or result in death or hospitalization, but may jeopardize the subject or may require intervention to prevent any of the SAEs defined above).

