#### **4.3.6 Primary Endpoint Analysis:**

The primary efficacy hypothesis test for the study is as follows:

Null Hypothesis: There is no difference between the treatment groups in the mean incidence of hypoglycemia (glucose  $\leq 70$  mg/dL (3.89 mmol/L)) associated with an exercise session occurring within the 12 weeks of out-patient treatment as measured by BGM.

Alternative Hypothesis: There is a difference between treatment groups in the mean incidence of hypoglycemia (glucose  $\leq 70$  mg/dL (3.89 mmol/L)) associated with an exercise session occurring within the 12 weeks of out-patient treatment as measured by BGM.

Incidence rate per subject is calculated by summing the number of exercise sessions completed within 12 weeks and dividing this denominator by the number of hypoglycemic events that

occurred during those exercise sessions (Incidence Rate = number of exercise sessions / inter/post-exercise hypoglycemic events). Events associated with an exercise session are defined as hypoglycemic events that occur during or within 30 minutes of exercise completion.

The primary efficacy analysis will be analyzed by ANOVA comparing the mean incidence rate between the three treatment groups. All statistical significance testing will be two-sided with a p-value  $<0.05$ . Efficacy endpoints will be analyzed using the ITT and PP analysis populations for Outpatient phase, if performed F-test yields an overall p-value less than 0.05 ( $p<0.05$ ), post-hoc analysis of groups means will be conducted to statistically determine which group means differ.

Parameters that do not meet normality criterion will be analyzed non-parametrically. Overall treatment effect will be assessed using Friedman's test. If the overall treatment effect is significant in the Friedman's test, pairwise treatment comparisons will be assessed using the following tests.

- If the difference between two treatments is normally distributed (i.e., the p-value is  $\geq 0.05$  for Shapiro-Wilk test, the Tukey Test will be used.
- If the difference between two treatments is not normally distributed and the distribution is highly skewed, then the sign test/Kruskal Wallis test will be used.

Example of SAS syntax code that can be used for primary endpoint analysis is provided in APPENDIX 1.

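### The SAP admits outpatient sessions to the primary endpoint without any blood glucose meter reading after exercise starts, and has no rule for sessions that lack one

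*SAP*

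**What the plan says.** The primary endpoint is hypoglycemia at or below 70 mg/dL linked to an outpatient exercise session, measured by BGM. SAP section 3 says which sessions enter: "For primary endpoint analysis the exercise session must meet the criteria defined in Section 2.4 as being a 'qualified exercise session". The outpatient criteria, given in SAP 2.4 and repeated in section 3, are four:

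- "a confirmed blood glucose value of 100-180 mg/dL" before the start;
- injection within 10 minutes before exercise;
- an allowed activity lasting 30 to 75 minutes;
- the heart-rate target reached at least once.

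SAP 4.3.6 then counts sessions: "Incidence rate per subject is calculated by summing the number of exercise sessions completed within 12 weeks". It counts events in a fixed window: "Events associated with an exercise session are defined as hypoglycemic events that occur during or within 30 minutes of exercise completion". Neither count depends on a reading having been taken in that window. The per-protocol definition in SAP 4.1 adds no such condition.

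Protocol 10.4.1 sets the schedule: "The subject will take 5 BGM measurements with exercise". Three of the five fall after the start: 30 minutes in, at the end, and 30 minutes after the end. This is an instruction to the subject, not a condition for the session to count. The same section has the subject use the meter to check a CGM value at or below 70 mg/dL.

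On missing data, Protocol 12.4.10 says the primary and secondary endpoints will be "reviewed for missing data and appropriate methodology applied if applicable, as described in the SAP". SAP 2.2 answers "Imputation of missing data will not be performed" and then covers only adverse event and medication dates and two adverse event flags. The one substitute for a missing reading, "If BGM readings are missing from the CRC phase, the YSI readings can be used", is limited to the clinic phase.

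**The concern.** A subject can check glucose, inject, exercise for 40 minutes and take no further fingerstick. That session meets all four criteria. It adds one to the session count and cannot add an event, so it counts the same as a session measured three times and found normal. A partly read session has a milder form of the problem: one normal value at 30 minutes leaves the end and post-exercise time points unmeasured but event-free.

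The outcome readings are self-taken away from the clinic by subjects who can see their CGM. One of the three arms is open-label, and its subjects know they have injected glucagon. Testing effort could therefore differ between arms, and the primary F-test could then respond to testing effort as well as to hypoglycemia. Both the ITT and the per-protocol analysis are exposed. SAP 5 plans a listing of outpatient BGM values, but no table that counts sessions without outcome readings.

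**Working it through.** **Inputs.**

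- Variance of means 59, common SD 15, 14 per arm, 80% power, alpha 0.05 (Protocol 12.2, SAP 1.3). I read 59 and 15 as being on a percentage-point scale.
- Two to three sessions a week for 12 weeks (Protocol 8.4), so 24 to 36 per subject; 30 is used below.
- Illustrative true rate p = 5/15 = 33.3%, from the insulin-reduction condition of XSMP-203 (Protocol 4.2).
- Share of sessions unread, m: not in the documents. Values of 5% to 30% are assumptions.
- Rates are taken as events divided by sessions. SAP 4.3.6 prints the ratio the other way up, which is a separate defect. Under the printed form an unread session raises the ratio instead of lowering it.

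**1. The plan's own figure.** Effect size = 59/15² = 0.262. With three groups and noncentrality 3n × 59/225, power is 0.789 at n = 13 and 0.823 at n = 14, so 14 per arm reproduces. For equally spaced means (−d, 0, d), 2d²/3 = 59 gives d = 9.4 and a range of 18.8 points. For one arm against two equal arms, 2D²/9 = 59 gives D = 16.3 points.

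**2. Skipping unrelated to glucose.** The expected observed rate is p(1 − m).

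- 10% unread: 33.3 × 0.9 = 30.0%.
- 30% unread: 33.3 × 0.7 = 23.3%.
- False difference: 30.0 − 23.3 = 6.7 points, with no true difference.

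**3. Every low confirmed by meter, only normal sessions skipped.** Take 10% versus 30% of the normal sessions as unread.

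- Planned count: 33.3% in both arms, so no bias.
- Evaluable sessions only: 0.333/(0.333 + 0.667 × 0.9) = 0.333/0.933 = 35.7%, against 0.333/(0.333 + 0.667 × 0.7) = 0.333/0.800 = 41.7%.
- False difference: 6.0 points, now caused by the exclusion.

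**4. Effect on the test, under step 2 only.** This is a beta-binomial simulation with 14 per arm, 30 sessions, between-subject SD about 15 points and 20,000 runs, with readings missing at random within arm.

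| True rates (%) | Unread by arm (%) | Rejection rate, planned count | Rejection rate, evaluable sessions only |
|---|---|---|---|
| 33/33/33 | 5/5/20 | 0.143 | 0.050 |
| 33/33/33 | 10/10/30 | 0.244 | 0.050 |
| 33/17/17 | 0/0/0 | 0.81 | 0.82 |
| 33/17/17 | 20/20/20 | 0.78 | 0.79 |
| 33/17/17 | 30/10/10 | 0.37 | 0.79 |

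Equal missingness lowers every rate but costs little power, because the spread between subjects shrinks too. Unequal missingness does the damage.

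**The case against.** The strongest reply is that the SAP nowhere says an unread session is event-free. The endpoint is defined as measured by BGM, and SAP 2.2 forbids imputation, so a programmer could reasonably treat an unread session as missing. This stands in part. The scoring is an inference from the counting rules, not a written instruction. But no passage removes such a session from the count, and the handling of a primary outcome should not be left to the programmer.

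Second, there is a safeguard. Protocol 10.4.1 has subjects confirm a low CGM value by meter, so a low is more likely than a normal value to leave a BGM record. Meter data are also downloaded at each visit (Protocol Table 1, note k), which makes gaps visible. This stands, and it matters: p(1 − m) holds only if skipping is independent of glucose, and step 3 shows the planned count is unbiased in the opposite case. The safeguard is still not a condition for a session to count, and visible gaps do not supply an analysis rule.

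Third, every missingness rate is assumed, and the open-label argument does not reach the comparison of placebo with glucagon plus basal reduction, which is blinded. Both are correct. The omnibus F-test nevertheless includes the open-label arm.

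Fourth, the CGM secondary endpoints over 0 to 300 minutes do not depend on fingersticks, and Protocol 12.4.10 permits sensitivity analyses. These help interpretation, but none is specified for unread sessions in the primary endpoint.

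**Conclusion.** The gap is real and bears on the primary result. An outpatient session can enter the count with no outcome reading, no passage makes it non-evaluable, and the count as written works as an imputation of no event. The size is unknown because the documents give no rate of missed readings. In the illustrations it is 6 to 7 points at an assumed 10% versus 30% unread, against a planned spread of about 16 to 19 points. The main risk is unread sessions that differ by arm. If they are equal across arms, the cost in power is small.

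A reader might go further and infer that the SAP directs unread sessions to be scored as normal, that the trial is therefore biased towards glucagon, or that excluding unread sessions is simply the unbiased answer. The documents support none of these. The scoring is implied, not stated. Nothing shows which arm would test less. The direction of bias depends on whether skipping is related to glucose: exclusion removes the bias in one case and creates it in the other.

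**What to change.** In SAP 3 and 4.3.6, before unblinding:

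- Define an evaluable session as a qualified session with at least one non-control BGM reading between the start of exercise and 30 minutes after its end.
- Tabulate by arm the sessions with no such reading and those with only some of the scheduled readings.
- Report the primary comparison both with evaluable sessions only and with all qualified sessions. Name in advance which of the two carries the formal test.
- Pre-specify an analysis of all qualified sessions in which CGM in the same window classifies those without BGM.
- Treat the primary conclusion as robust only if these analyses agree.

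The cost is SAP wording, one table and additional runs on time-stamped BGM and CGM data already being collected; study conduct does not change. One analysis rests on slightly fewer sessions. The evaluable-only analysis can suffer selection if subjects skip tests when CGM looks normal. The CGM-filled analysis is there to show this, with the limit that CGM reads interstitial glucose and is not the meter named in the endpoint.

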**Qualified Exercise Session:** For inclusion in the statistical analysis for the per protocol population (defined in section 4.1) a qualified exercise session will be defined. Exercise sessions will be performed in both the CRC and Outpatient phases. In the CRC phase, a qualified exercise session will be defined as the subject having (1) a blood glucose value of 100-180 mg/dL (5.56 - 10 mmol/L) prior to starting exercise, (2) completed 45 minutes of exercise (not including breaks), (3) achieved a target heart rate of 80% of maximum calculated heart rate at least once during the workout session, and (4) fasted at least 8 hours prior to that exercise session.

Primary analysis in the CRC Phase will be based on the above definition of qualified exercise session. Additional subgroup analysis will be applied to analyze exercise sessions in which subjects achieved a target heart rate of 80% of maximum calculated heart rate for 30% and 50% of the exercise time.

In Outpatient phase, a qualified exercise session will be defined as the subject having (1) a confirmed blood glucose value of 100-180 mg/dL (5.56 - 10 mmol/L) prior to starting exercise, (2) self-administered the study drug no more than 10 minutes prior to exercise (five minutes is the target), (3) conducted a protocol allowed exercise for moderate to high intensity for at least 30 minutes and no longer than 75 minutes, and (4) achieved a target heart rate of 80% of maximum calculated heart rate at least once during the session. If a subject has more than one exercise session in a day that is deemed a qualified exercise session, only the first qualified exercise session that day will be used in the analysis.

Primary analysis in the Outpatient Phase will be based on the above definition of qualified exercise session. Additional subgroup analysis will be applied to analyze exercise sessions in which subjects achieved a target heart rate of 80% of maximum calculated heart rate for 30% and 50% of the exercise time.

**Target Heart Rate:** Per protocol, the goal is to achieve a target of 80% of maximum calculated heart rate during the session as shown by the following equation:

- Target Heart Rate =  $0.80 \times (220 - \text{Age in Years})$

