## 4. STATISTICAL METHODOLOGY

### 4.1 Definition of Analysis Population

**All Screened Subjects:** All Screened subjects will include any subject who signed the informed consent form.

**Intention to Treat (ITT) Population:** All randomized subjects regardless of whether they received Study Drug.

**Per Protocol (PP) Population:** ITT participants who completed a qualified exercise session, and who was dosed within the study window and did not meet any of the key exclusion criteria at screening. The definition of qualified exercise is defined in Section 2.4.

**Safety Population:** All randomized subjects who received any amount of Study Drug.

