### **4.4 CHANGES FROM PROTOCOL**

NA

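### The primary session rule requires 30 minutes of achieved exercise, so a correctly dosed session stopped earlier for hypoglycemia is dropped because it had the primary event

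*SAP*

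**What the plan says.** **Session rule.** SAP 3 (Primary Endpoint) states: "For primary endpoint analysis the exercise session must meet the criteria defined in Section 2.4". Four criteria follow: a pre-exercise glucose of 100-180 mg/dL; dosing no more than 10 minutes before exercise; that the subject "conducted a protocol allowed exercise for moderate to high intensity for at least 30 minutes and no longer than 75 minutes"; and 80% of calculated maximum heart rate reached at least once. The last two describe what happened after dosing. SAP 2.4 gives the same definition and adds that only the first qualified session of a day is used. Neither section makes an exception for a session stopped because of hypoglycemia.

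**Stop rule.** Protocol 10.4.1 requires an outpatient session to stop if glucose falls to 70 mg/dL or below, and bars further exercise that day. The same threshold defines the primary event.

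**Dosing rule.** Protocol 10.4.1 and Appendix 1 base dosing on planned duration (30-75 minutes); Appendix 1 also requires planned intensity.

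**Scope of the filter.** SAP 2.4 introduces the qualified session with the words "For inclusion in the statistical analysis for the per protocol population", but later says "Primary analysis in the Outpatient Phase will be based on the above definition of qualified exercise session". SAP 4.1 uses the term only in the PP definition: "ITT participants who completed a qualified exercise session, and who was dosed within the study window". SAP 4.3.6 builds each subject's rate by "summing the number of exercise sessions completed within 12 weeks", does not use the term qualified, and analyses both ITT and PP. SAP 2.2 states: "Imputation of missing data will not be performed". The entry under "CHANGES FROM PROTOCOL" (SAP 4.4) is NA.

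**The concern.** A session stopped at minute 20 for confirmed hypoglycemia was properly dosed under the protocol, had the primary event, and cannot reach 30 minutes that day. Under SAP 2.4 and 3 it is counted neither as a session nor as an event. The heart-rate criterion can act the same way, because a session cut short may end before the target is reached. The primary analysis is then selected on its own outcome, after randomisation, and the lost share may differ between arms.

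The second issue is which sessions make up the ITT analysis. Two programmers could read SAP 2.4, 3, 4.1 and 4.3.6 differently and derive different ITT rates from the same data. If the filter applies to ITT, a randomised subject with no qualified session has no rate and, without imputation, drops out of the ITT ANOVA.

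**Working it through.** **1. The plan's own sample size.** Inputs from SAP 1.3: variance of means 59, common SD 15, alpha 0.05, one-way ANOVA with three groups.

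- Effect size = 59 / 15² = 59 / 225 = 0.262.
- Noncentrality = 3 × n × 0.262, with 2 and 3(n − 1) degrees of freedom.
- Power is 78.9% at n = 13 and 82.3% at n = 14, so the stated 14 per group is reproduced.

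**2. Rates consistent with that variance.** Assume the two glucagon arms are equal. A gap d between control and each glucagon arm gives a variance of means of (2/9)d². Setting this to 59 gives d = √(59 × 9/2) = 16.3 points. An assumed control rate of 25% then implies 8.7% in each glucagon arm.

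**3. Effect of dropping early-stopped event sessions.** Take the rate as events per session, with at most one event per session. (SAP 4.3.6 prints the ratio the other way up, which is a separate matter.) If p is the true rate and q the share of event sessions stopped before 30 minutes:

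observed rate = p(1 − q) / (1 − pq)

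For one subject with 30 dosed sessions and 6 event sessions, the true rate is 6/30 = 20.0%. Dropping one early stop gives 5/29 = 17.2%; dropping three gives 3/27 = 11.1%.

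**4. Effect on the comparison.** SD stays at 15 with 14 per arm. Every q is assumed, because the documents give none.

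| q, equal in all arms | Control | Each glucagon arm | Gap (points) | Power |
|---|---|---|---|---|
| 0% | 25.0% | 8.7% | 16.3 | 82% |
| 2% | 24.6% | 8.5% | 16.1 | 81% |
| 5% | 24.1% | 8.3% | 15.7 | 79% |
| 10% | 23.1% | 7.9% | 15.2 | 76% |

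With unequal q:

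- q = 30% in control and 0 in glucagon: 0.175/0.925 = 18.9% against 8.7%, a gap of 10.2 points.
- q = 10% in control and 30% in glucagon: 23.1% against 0.0609/0.9739 = 6.3%, a gap of 16.8 points.

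Equal loss shrinks the contrast. Unequal loss can shrink or enlarge it.

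**5. How an early event can be seen.** The first scheduled in-exercise meter reading is at 30 minutes, with a ±2 minute window (Protocol 10.4.1), and Protocol 9.1.1 has the Fitbit time the 30-minute periods. Events before 30 minutes therefore come mainly from meter checks prompted by the unblinded CGM or by symptoms, and otherwise from a scheduled reading taken slightly early. The documents give no frequency for either.

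**6. What is still counted.** A session that reaches 30 minutes and the heart-rate target before stopping still qualifies, and events within 30 minutes after exercise count. Only early events are lost. The planned subgroups requiring target heart rate for 30% or 50% of exercise time tighten the filter and restore nothing.

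**The case against.** **Delegation.** Protocol 12.3 leaves the definition of qualified exercise to the SAP, so a reader who infers that the SAP silently overrode the protocol goes too far. Protocol 12.3 and 12.4.1 themselves speak of completed sessions. But the delegation sits within the PP definition, and the protocol nowhere limits the primary endpoint to qualified sessions. That extension belongs in SAP 4.4.

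**Scope.** SAP 3 read literally already covers ITT: ITT selects subjects, the session rule selects sessions, and the two can coexist. It would therefore be too strong to say that the ITT analysis is undefined. What stands is a wording conflict that must be reconciled.

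**Materiality.** A reader might infer that many events are lost, or that the result is biased in a known direction. The documents support neither. The first scheduled reading coincides with the 30-minute threshold, and a device timer favours readings at or near it. If q is 2%, the illustration barely moves. This objection stands and limits how serious the point is.

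**Remedy.** A wider session set brings in exercise that is shorter, longer or less intense than intended, and can cost power. That is true, and the cost is shown with the fix. The argument for the change is a session set that does not depend on the outcome, not a gain in power.

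**Conclusion.** The text gap is certain. SAP 2.4 and 3, combined with the stop rule in Protocol 10.4.1, exclude a correctly dosed session because it had an early primary event, and nothing in either document restores it. Whether the same filter governs ITT needs one consistent statement.

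The size and direction of the effect are not known. The illustrated loss, from 82% power to 81, 79 or 76% at q of 2, 5 or 10%, rests on an assumed q equal in all arms, assumed rates of 25/8.7/8.7%, an unchanged SD of 15 and 14 subjects per arm. This should be fixed before the data are unblinded. The documents do not show that it would change the trial's conclusion.

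**What to change.** Change analysis definitions only; the clinical stop rule is not at issue.

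- **Primary ITT session set (SAP 2.4, 3 and 4.3.6).** Use criteria fixed before the outcome: a dosed session of protocol-allowed exercise, pre-exercise meter glucose of 100-180 mg/dL, dose no more than 10 minutes before exercise, and the first such session of the day. Include it whatever the achieved duration or heart rate.
- **Planned duration.** This is the protocol's dosing condition, but it is not among the diary items listed in Protocol 10.4.1. Treat a dosed session as planned to qualify, and say so.
- **PP or sensitivity analysis.** Keep the achieved-duration and heart-rate criteria here, labelled as conditioned on conduct after dosing. Optionally add a sensitivity analysis that readmits only sessions stopped for hypoglycemia, noting its upward bias: short sessions without an event stay out.
- **Reporting.** State which session set applies to ITT and which to PP. Report the number of ITT subjects with no eligible session; the new rule does not give them a rate. Record the change in SAP 4.4.

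**Cost.** This takes SAP wording and one derivation rule, using data already collected: diary dose and exercise times, meter timestamps and Fitbit records. Some shorter, longer or lower-intensity sessions enter ITT. If 20% of dosed sessions (assumed) miss the achieved criteria and carry a fraction r of the event risk, each rate is multiplied by 0.8 + 0.2r:

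- r = 0.5: 22.5% against 7.8%, gap 14.7 points, power 73%.
- r = 0.75: 23.8% against 8.3%, gap 15.5 points, power 78%.
- r = 1: 25.0% against 8.7%, gap 16.3 points, power 82%.
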